5. Research involving materials (data, documents, records, or specimens) that have been collected, or will be collected solely for nonresearch purposes (such as medical treatment or diagnosis). (NOTE: Some research in this category may be exempt from the HHS regulations for the protection of human subjects. 45CFR 46.101(b)(4). This listing refers only to research that is not exempt.)

**Protocol Title:** Smoking Cessation Following Text Message Intervention in Pregnant Women

---

6. Collection of data from voice, video, digital, or image recordings made for research purposes.
7. Research on individual or group characteristics or behavior (including, but not limited to, research on perception, cognition, motivation, identity, language, communication, cultural beliefs or practices, and social behavior) or research employing survey, interview, oral history, focus group, program evaluation, human factors evaluation, or quality assurance methodologies. (NOTE: Some research in this category may be exempt from the HHS regulations for the protection of human subjects. 45 CFR 46.101(b)(2) and (b)(3). This listing refers only to research that is not exempt.)
- X 8. [FOR IRB use only]. Continuing review of research previously approved by a convened IRB only when condition (a), (b), or (c) is met.
- a) Previously approved research where
- (i) The research is permanently closed to the enrollment of new subjects;
- (ii) All subjects have completed all research-related interventions; and
- (iii) The research remains active only for the long term follow-up of subjects.
- b) Previously approved research where no subjects have been enrolled and no additional risks have been identified.
- X c) Previously approved research where the remaining research activities are limited to data analysis.
9. [FOR IRB use only]. Continuing review or research not conducted under an investigational new drug application or investigational drug exemption where expedited categories two (2) through eight (8) do not apply but the IRB has determined and documented at a convened meeting that the research involves no greater than minimal risk and no additional risks have been identified.

---

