**If No, explain what SLU will NOT participate in:**

**Please save frequently**

Page numbers from a sponsor's protocol/grant may be referenced in 3b, 3c, and 3d.

- b) **Describe all the procedures, from screening through end-of-study, that the human subject must undergo in the research project, including study visits, drug treatments, randomization and the procedures that are part of standard of care. Specify which procedures are for research and which are standard of care. Please note: The box below is for text only. If you would like to add tables, charts, etc., attach those files in the Attachment section (#16).**

This is a randomized, open-label, prospective trial that will evaluate the impact of texting to pregnant, underserved, cigarette smokers on smoking cessation rates. It will be conducted over 18-months, with subject recruitment over 12 months, at St. Mary's Health Center Maternal Fetal Care Center. Potential patients will be identified through EPIC chart review as well as from referrals from providers. These patients will be screened for inclusion and exclusion criteria through a chart review as well as meeting with pharmacy to determine the patient's stage of change and willingness to set a quit date within the next 30 days. Informed consent will be obtained if the patient is eligible and willing to participate.

As part of routine care at the Maternal Fetal Care Center, pregnant women that are active smokers are encouraged to quit. If the patient is interested in quitting smoking, the physician or pharmacist will schedule a smoking-cessation consultation visit with maternal-fetal clinical pharmacist. During this pilot study, women who have expressed interest in quitting and meet the inclusion and exclusion criteria will be approached and offered enrollment in the smoking cessation study. Patients who consent will be randomized to either the texting group or control group. For randomization purposes, an equal number of notecards will be made for the two groups. We will use a random number generator to help with patient randomization. These

**Protocol Title:** Smoking Cessation Following Text Message Intervention in Pregnant Women

---

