groups. We will use a random number generator to help with patient randomization. These numbers will be placed in a sealed envelope and shuffled. At the time of patient inclusion, an envelope will be selected by the pharmacist. However, if a patient declines receiving text messages but consents to participate in the pharmacist driven CBT and NRT, she will be enrolled in the standard of care group. A baseline carbon monoxide level will be obtained.

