If available, delivery details will be abstracted from the patient charts and shall include gestational age at delivery, fetal weight, APGAR scores, and umbilical cord gases.

- c) **If the proposed study is a clinical trial where a drug, vaccine, device or other treatment is compared to a placebo group or comparison treatment group, what are the guidelines or endpoints by which early decisions regarding efficacy or lack of efficacy can be made? For example, it may be reasonable to stop enrollment on a study when efficacy has already been clearly demonstrated, to avoid unnecessary enrollments of additional subjects. Alternatively, it may be reasonable to stop enrollment when it is clear that efficacy will never be demonstrated, given the statistical power of the study as designed. Describe the guidelines that are in place to assist in making these determinations, if relevant to the proposed study.**

N/A

- d) **Describe how data analysis will be performed (statistical tests, methods of evaluating data) and indicate the smallest group/unit for which separate reporting will occur. For studies involving a questionnaire, if data and reliability information are available, please describe or provide references. For full board, unfunded studies describe sample size determination and power analysis. If none, please justify.**

Power Calculation

Based on previous experience, we anticipate 30% of patients will stop smoking at 2 weeks and anticipate texting will increase cessation rates by an additional 5%. Using G\*Power, based on a Chi square test, alpha of 0.05, power of 0.8, and medium effect size of 0.5, we estimate needing 52 patients. We anticipate 15% lost to follow-up or drop outs, so we anticipate needing 60 patients for this pilot project.

G\*Power is a free online statistical tool for calculating power in social, behavioral, and biomedical sciences.

Outcomes and Statistical Analysis

Primary Outcome- Smoking cessation rate verified by exhaled carbon monoxide levels (<8ppm) at 2weeks of quit date between texting and control group

Statistical Analysis- Chi-squared or Fischer's Exact Adjusted for confounders: multiregression

**Protocol Title:** Smoking Cessation Following Text Message Intervention in Pregnant Women

---

Statistical Analysis- Chi-squared or Fischer’s Exact Adjusted for confounders: multiregression analysis

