**Identify inclusion criteria.**

Have a confirmed pregnancy,  
Obstetric care provided at the St. Mary's Health Center Maternal Fetal Care Center,  
English speaking,  
18-55 years of age,  
Are in the preparation stage of change and willing to set a quit date within 30 days and before 35 weeks gestation,  
Have a cellular phone that is capable of receiving text messages, and be willing to pay for any related fees for testing.  
Willing and able to commit to the visit schedule

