**Identify exclusion criteria.**

Gestational age > 35 weeks at quit date  
If subjects are in the pre-contemplative or contemplative stages of change or have already received 30

**Protocol Title:** Smoking Cessation Following Text Message Intervention in Pregnant Women

---

minute pharmacy education targeted for the quit date in this pregnancy.

- i) **Compensation. Explain the amount and schedule of compensation, if any, that will be paid for participation in the study. Include provisions for prorating payment.**

No compensation will be paid to the subject

- j) **Describe who will cover study related costs. Explain any costs that will be charged to the subject.**

The carbon monoxide testing will be paid for by St. Louis College of Pharmacy.

All pharmacotherapy, although standard of care will be provided by the College of Pharmacy.  
All visits are standard of care and will not be paid for by the study.  
Subjects will be advised prior to consenting that if their phone plan charges for receiving text messages, the study will not pay for those charges.  
No study related costs will be billed to the subject or their insurance.

- k) **Estimate the probable duration of the entire study including data analysis and publication. This estimate should include the total time each subject is to be involved and the duration the data about the subject is to be collected. If the study is Investigator-initiated, a timeline for individual subject recruitment, follow-up, total time for subject accrual, and data analysis for the study is required.**

Subject participation will vary depending on when in her pregnancy a subject enrolls.  
March 2014: Obtain IRB approval  
April 1 2014: Begin enrolling patients via randomization  
April 31st, 2015: Cease enrollment of new patients  
June 1st 2015: Final collection of all data for all enrolled patients  
Summer 2015: Data analysis, manuscript preparation

---

\* \* \* Risks \* \* \*

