**b) Hardcopy (Paper) Data**

Click "Add" to enter information for each type of hardcopy (paper) data that will be created in the study: anonymous/de-identified, coded, and/or identifiable (see definitions above).

To properly address this question, there should only be one listing of each type of data in the table. Depending on your project, you could have up to three types of data.

Not Applicable, No Hardcopy (Paper) Data

Study IRB-approved Prior to New Question (Question N/A- Grandfathered)

**c) If a master list is used in this study (linking study codes to subject identifiers), explain: a) how and where you will secure the master list, b) how long it will be kept/when it will be destroyed, and c) provide a sample of the code.**

Code numbers will be used to link the subject to their data. Code and identifiers will be kept separate. PHI will be password protected behind a firewall. Paper copies will be kept in a locked cabinet, in a locked

**Protocol Title:** Smoking Cessation Following Text Message Intervention in Pregnant Women

---

office, in a locked suite.

After data is entered into the database, the paper copy of the data will be destroyed.

A master list is kept to link the medical record information to the subject and to obtain follow up information (delivery). The master list is kept separate from the data and will be destroyed when the study is complete.

**d)&n bsp If data or specimens are being shared outside of the research team, indicate who will receive the material and specifically what they will receive (data or specimens).**

The only patient information stored in the Google Voice system will be a phone number which will be identified by a unique participation number for each patient upon her inclusion in the study. The Google Voice system is password protected and only one person will have the password.

The St. Louis College of Pharmacy's IRB provides oversight and may require review of the research records, including patient information.

**e) If samples or data will be provided from an outside source, indicate whether you will have access to identifiers, and if so, how identifiable information is protected.**

N/A

**f) If data will be collected via e-mail or the Internet, how will anonymity or confidentiality be affected? Describe how data will be recorded (i.e., will internet protocol (IP) addresses and/or e-mail addresses be removed from data?).**

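### Women who decline texts are placed in control, so the primary comparison is not fully randomised and can be biased in either direction

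*Combined protocol and SAP*

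**What the plan says.** Section 3b states "Patients who consent will be randomized to either the texting group or control group", using equal numbers of cards in sealed, shuffled envelopes, one of which the pharmacist selects at inclusion. It then makes an exception for any woman who "declines receiving text messages but consents to participate in the pharmacist driven CBT and NRT, she will be enrolled in the standard of care group". It does not say whether she declines before or after the envelope is drawn. Section 9, item 7, describes the control group as the one receiving standard of care, so the two names refer to the same arm.

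Section 3d defines the primary outcome as "Smoking cessation rate verified by exhaled carbon monoxide levels (<8ppm) at 2weeks of quit date between texting and control group", tested by chi-squared or Fisher's exact test, with a further analysis "Adjusted for confounders: multiregression analysis". It lists no covariates and names no analysis population, decliner flag or exclusion.

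The inclusion criteria in section 8h require a phone that can receive texts and that the woman "be willing to pay for any related fees for testing". They do not list willingness to receive texts. Section 8j says women will be told before consent that "if their phone plan charges for receiving text messages, the study will not pay for those charges".

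**The concern.** Randomisation makes the arms comparable only if every woman in the comparison reached her arm by chance. Here control can hold two kinds of women, those whose envelope said control and those who did not want texts, while texting holds only women who accepted them. A woman may decline because she is less motivated to quit, or only because her phone plan charges for messages. The first reason would make texting look better than it is; the second need not. The resulting error in the primary estimate is systematic, so enrolling more women does not reduce it. The planned regression is no assured remedy, because its covariates are unnamed and it can adjust only for what was measured.

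**Working it through.** **Inputs.** From section 3d: a 30% quit rate at 2 weeks, a planned gain of 5 points, and 60 women (52 × 1.15 = 59.8, rounded up). From section 3b: 1:1 allocation. From section 8b: 100 women, used as a second sample size. Assumed, because the documents are silent: a share *d* of women declining (10%, 20%, 30%), a decliner quit rate *q* (10% to 50%), acceptors quitting at 30% in both arms, and no true effect of texting.

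**If women decline before the draw, N = 60.** Texting has 30(1 − d) women at 30%. Control has 30(1 − d) acceptors plus 60d decliners, which is 30(1 + d) women, with quit rate [30(1 − d) × 0.30 + 60d × q] / [30(1 + d)].

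**If they decline after the draw.** Decliners who drew texting (30d) move to control, and would-be decliners who drew control (30d) are already there. Control again holds 60d decliners among 30(1 + d) women.

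**Both cases give the same result:** false difference (texting − control) = 2d(0.30 − q)/(1 + d). N cancels, so 60 and 100 women give the same bias.

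Check at d = 0.20, q = 0.10: texting is 30.0% of 24. Control is (24 × 0.30 + 12 × 0.10)/36 = 8.4/36 = 23.3%. The difference is +6.7 points.

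| Decliners quit at | 10% decline | 20% decline | 30% decline |
|---|---|---|---|
| 10% | +3.6 | +6.7 | +9.2 |
| 20% | +1.8 | +3.3 | +4.6 |
| 30% | 0 | 0 | 0 |
| 40% | −1.8 | −3.3 | −4.6 |
| 50% | −3.6 | −6.7 | −9.2 |

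**Decliners needed for a false 5 points.** At q = 0.15, solve 2d × 0.15/(1 + d) = 0.05. This gives d = 0.05/(0.30 − 0.05) = 0.20, or 12 of 60 women.

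**Effect on the test.** These are false-positive rates of the uncorrected chi-square test at 0.05, by exact enumeration with fixed arm sizes (27/33, 24/36 and 21/39 at N = 60; 45/55, 40/60 and 35/65 at N = 100). The three columns are the share declining.

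| | 10% | 20% | 30% |
|---|---|---|---|
| N = 60, decliners quit at 10% | 5.6% | 8.8% | 13.4% |
| N = 100, decliners quit at 10% | 8.1% | 11.7% | 19.3% |

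At N = 60 the range is 5.0–7.2% if decliners quit at 20% and 5.2–5.8% if they quit at 40%. With no decliners the rate is 4.9% at 30 per arm and 5.0% at 50 per arm. Arms of 45 and 55 give 5.7% with no bias at all, so not all of the 8.1% is selection.

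**Would a decliner flag be enough?** If women decline before the draw, yes: dropping them leaves a randomised comparison. If they decline after it, no, because women who drew control and would have declined are never identified. Dropping only the flagged women leaves control at (1 − d) × 0.30 + d × q. At d = 0.20 and q = 0.10 that is 26%, still a false difference of 4 points. Analysing those women in the arm they drew removes the bias.

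**The case against.** The rule may rarely or never have been used. If nobody declined, or decliners quit at the same rate as others, the bias is zero. Decliners may be few: women are told about text charges before consent, and if the word testing in the section 8h fee criterion was meant as texting, women unwilling to pay would already be ineligible. With one or two decliners among 60 quitting at 10%, the formula gives only 0.7 or 1.3 points. The study is also described as a pilot. At 60 women the standard error of the difference is 11.8 points, so a bias of 1.8 to 3.6 points is about 0.15 to 0.3 of a standard error. The data collection sheets, which are attachments not seen here, may record both the envelope and the refusal.

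All of that is fair as to size. None of it removes the defect. Section 8h does not require willingness to receive texts, and section 3b expressly admits women who refuse them, so the two need reconciling however the fee wording is read. A pilot estimate that carries selection would also mislead the planning of a later trial. Counting the decliners is the inexpensive way to show that there were none.

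**Conclusion.** The concern holds. Followed as written, the plan lets self-selected women into control, and nothing in section 3d takes them out again. That is certain from the text; the size and direction of the bias are not. Under the stated assumptions (acceptors at 30%, no texting effect, 10% to 30% declining, decliners quitting at 10% to 50%) the false difference runs from −9.2 to +9.2 points, so it can equal or exceed the planned 5 points. The effect on the false-positive rate is more modest, especially at 60 women. This must be fixed, because it affects the validity of the primary comparison and a larger sample cannot cure it.

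**What to change.** **Analysis first.** The Expedited Paragraphs section has category 8(c) marked: "Previously approved research where the remaining research activities are limited to data analysis". State in section 3d that the primary analysis includes only women allocated by envelope, each analysed in the arm drawn. Flag and count the women who declined texts, by whether they declined before or after the draw. Report those who declined before it separately, as a non-randomised group.

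Confirm that the database holds both the envelope drawn and the refusal, since section 11c says "After data is entered into the database, the paper copy of the data will be destroyed". If it does not, say so, do not present the comparison as fully randomised, and show the result over a range of assumed decliner numbers and quit rates above and below 30%.

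**If enrolment is still open,** make willingness to receive texts an eligibility condition confirmed before the draw (sections 3b and 8h) and reconcile it with the fee wording in 8h. Follow decliners under the usual care already described, outside every between-arm comparison.

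**Cost.** One or two sentences in 3d and a check of the allocation records, plus one sentence each in 3b and 8h if enrolment is open. Section 3b ties free pharmacotherapy to consenting participants, so the documents would then also need to make clear where decliners stand.

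The comparison also loses some precision or contrast:

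- If 10%, 20% or 30% of 60 decline before the draw, 54, 48 or 42 women remain. The standard error, √(2 × 0.30 × 0.70/(n/2)), rises from 11.8 to 12.5, 13.2 or 14.1 points.
- If they decline after the draw and are analysed as randomised, a 5-point effect in acceptors is diluted to 5 × (1 − d) = 4.5, 4.0 or 3.5 points, assuming texting has no effect in decliners.

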#### Description of Usual Care

The patient, regardless of group, will have the standard of care smoking cessation visit with the clinical pharmacy specialist or PGY2 ambulatory care resident. The visit will include

- Medication reconciliation
- Review social history which includes use of street drugs and alcohol, allergies, and vaccine history
- Obtain smoking history that included current amount smoking, changes in smoking habits during this pregnancy, number of years smoked, quit attempt history, and use of previous smoking cessation aids
- Design a quit plan that includes setting a quit date within the next 30 days, obtain follow-up contact information, identify motivators/triggers/barriers, discuss withdrawal symptoms, develop plan for management of withdrawal symptoms, develop a plan for behavior modifications, discuss rewards, handling of relapse, medication options for cessation during pregnancy, and education on purpose, proper use, potential maternal and neonatal adverse events

If the pharmacist, physician, and patient deem that pharmacotherapy is appropriate, the patient will receive a 2 week supply if using NRT or 3 week supply if using bupropion. The smoking cessation pharmacotherapy will be supplied free of charge to the consenting participants. If the patient is prescribed NRT patches, the medication will be provided in two week intervals. If the patient is prescribed bupropion, the medication will be provided for a 3 week supply with the initial dispensing and 2 week supply thereafter. Dosing and length of treatment will follow package insert approved dosing. Patients will receive a voucher to take to the Clayton Health Services Pharmacy located across the street from the Maternal Fetal Care Clinic to receive either medication at no cost.

Demographics, social history, gestation age at enrollment, estimated due date, medications at enrollment, past medical history, and obstetric history include gravity and parity will be obtained from the EPIC medical record. Patients will be asked about smoking history, time to first morning cigarette, previous quit attempts, previous experience with cessation pharmacotherapy, motivators, triggers, and barriers during initial visit.

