Studies have proven that exposure to tobacco can increase the risk for placental abruption, placental previa, preterm birth, antenatal death, sudden infant death syndromes, attention-deficit/hyperactivity disorder and asthma.2-8 Compared to children of non-smoking mothers, children of mothers who smoked during pregnancy had a higher BMI and increased odds for being overweight at 4-years of age; however, in the children whose mother quit smoking during pregnancy there was no increased risk of increased BMI or being overweight compared to the children of non-smoking mothers.10 According to the data from the 2009 Pregnancy Risk Assessment and Monitoring System (PRAMS) approximately 12.4% of pregnant women with live births reported smoking during the last three months of pregnancy (PRAMS).11 Of the 25% of women who smoked in the 3 months prior to pregnancy, 52% quit during pregnancy; of those, 44% relapsed within 6 months after delivery. The perinatal period presents a critical opportunity to educate and support the mother as she attempts quit.

Current studies evaluating rates of smoking cessation in pregnant women show less than ideal results. A primary analysis of 12 pooled trials found a median quit rate of 4.9% in women with usual care. This rate increased to 13.2% in patients that received tailored self-help intervention.12 To help increase compliance with cessation, studies have investigated new interventions as part of the usual care provided to pregnant patients that continue to smoke. One study looked at including a 15-minute video and provider prompting at baseline and one month. Although a higher percentage of patients in the intervention group had a higher 30-day abstinence rate at 2-months post baseline, the finding was not significant (26.1% vs 10.5%, p=0.12) although the study did not discuss if this was an appropriately powered sample size.13 Another study looking at the combination of smoking cessation education, physical activity counseling and supervised exercise found a 25% abstinence rate at 8-months gestation.14 The use of NRT has also been studied. One study found that CBT plus NRT verses CBT alone was effective at 7-weeks (24% vs 8%, p=0.02) and 38-weeks' gestation (18% vs 7%, p=0.04), unfortunately there was no benefit at 3-months post-partum (20% vs. 14%, p=0.55).15

The use of pharmacological aids for smoking cessation is recommended as a potential option

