## 2. Purpose of the study

- a) Provide a brief lay summary of the project in <200 words. The lay summary should be readily understandable to the general public.

We propose an 18-month, randomized, open-label evaluation of the impact of texting to pregnant, underserved, cigarette smokers on smoking cessation rates. Patients will be eligible if they have a confirmed pregnancy, obstetric care provided at the St. Mary's Health Center Maternal Fetal Care Center, are English speaking, at least 18 years of age, are in the preparation stage of change and willing to set a quit date within 30 days and before 35 weeks gestation, and have a cellular phone that is capable of receiving text messages. Patients will be randomized to either the texting group or control group. A baseline carbon monoxide level will be obtained. The patient, regardless of group, will have the standard of care smoking cessation visit. If the pharmacist, physician, and patient deem that pharmacotherapy is appropriate, they will receive nicotine replacement therapy patches or bupropion free of charge in 2-week intervals. Patients in the intervention group will receive text messages focused on smoking cessation and pregnancy. Patients will be seen on a bi-weekly schedule to obtain additional vouchers for patches or for bupropion, meet with the pharmacist, and complete a carbon monoxide exhalation test. These visits will be continued until the pharmacotherapy course is complete. Patient information on additional barriers to stop smoking will also be obtained including the ongoing use of marijuana and alcohol. This information is also collected as standard of care for all pregnant women seen by our group.

Page numbers from a sponsor's protocol/grant may be referenced in 2b and 2c.

- b) List your research objectives (specific aims & hypotheses of the study).

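### The envelope is opened before the discretionary pharmacotherapy decision, so knowledge of the arm can make initial medication use unequal; the likely bias is modest and reordering the steps would reduce it

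*Combined protocol and SAP*

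**What the plan says.** Section 3b describes an open-label randomised trial and states: "Patients who consent will be randomized to either the texting group or control group". On allocation it adds: "At the time of patient inclusion, an envelope will be selected by the pharmacist". The same paragraph closes with: "A baseline carbon monoxide level will be obtained". The lay summary in section 2a has the same order: "Patients will be randomized to either the texting group or control group. A baseline carbon monoxide level will be obtained".

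The next part of 3b, Description of Usual Care, has every woman attend the cessation visit whatever her group. It makes medication conditional: "If the pharmacist, physician, and patient deem that pharmacotherapy is appropriate", she receives patches or bupropion free of charge. Under Intervention Group, the first text goes out 2-3 days before the quit date.

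Other sections read differently. The primary objective (2b) and item 7 of section 9 (Risks) describe pharmacotherapy as part of the usual care given to both arms, with texting as the only addition.

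The Background cites one obstetric trial in which "CBT plus NRT verses CBT alone was effective at 7-weeks (24% vs 8%, p=0.02"). The same trial gave 18% vs 7% at 38 weeks' gestation and 20% vs 14% (p=0.55) at 3 months post-partum. Section 3d expects 30% cessation at 2 weeks, with 5 points more from texting, and plans a regression adjusted for confounders that it does not name.

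**The concern.** The comparison is meant to isolate texting, so it needs co-treatment to be alike in the two arms apart from anything the texts themselves cause. Here a discretionary co-treatment is chosen after allocation is known, by three parties who are not blinded, and one of them drew the envelope. The plan neither sets criteria for the choice that are independent of arm nor has it recorded beforehand. A pharmacist might press medication harder on a woman without texts, or a woman might decline it because texts are coming. Either would enter the result as if it were an effect of texting.

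Two consequences follow. First, medication is an obvious candidate for the unnamed confounders in 3d, but a choice made after allocation with the arm known can itself be affected by the arm. Adjusting for it would not cleanly remove the bias and could add some. Second, the 2-week visit is scheduled for the voucher refill, and CO is measured at voucher pick-up. A woman without medication has less reason to attend, so unequal uptake could also make verification of the primary outcome unequal.

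Only the initial decision is at issue. Refill reminders are among the texts, and later use that they prompt belongs to the intervention's effect.

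**Working it through.** **Order of events.** Sections 2a and 3b agree: consent, envelope, baseline CO, usual-care visit, medication decision, then texts from 2-3 days before the quit date. This is read from the order of narration. No section gives explicit timings, and none contradicts it.

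**Size.** The plan gives no figure for medication uptake or for this bias, so there is none to reproduce. Its sample-size calculation is not needed here.

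Inputs:
- Medication effect per treated woman, *e*, from the Background: 24 − 8 = 16 points (7 weeks); 18 − 7 = 11 points (38 weeks' gestation); 20 − 14 = 6 points (3 months post-partum).
- Texting effect sought, from 3d: 5 points (30% to 35%).
- Arm difference in initial uptake, *d*: not in the documents. I assume 10 to 30 points.

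Formulas: spurious arm difference = *e* × *d*; uptake difference that would mimic the target = 5 / *e*.

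| *e* | *d* = 10 | *d* = 20 | *d* = 30 | *d* needed for 5 points |
|---|---|---|---|---|
| 16 | 1.6 | 3.2 | 4.8 | 5/16 = 31 |
| 11 | 1.1 | 2.2 | 3.3 | 5/11 = 45 |
| 6 | 0.6 | 1.2 | 1.8 | 5/6 = 83 |

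All entries are percentage points.

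**Against sampling error.** With 30 per arm (60 in total, 3d), the standard error of the difference in quit rates is √(0.30×0.70/30 + 0.35×0.65/30) = √(0.00700 + 0.00758) = 0.121, about 12 points. Section 8b lists 100 subjects; with 50 per arm it is √(0.00420 + 0.00455) = 0.094, about 9 points. A 1.6-point bias is small beside either. Unlike sampling error, it would not shrink as numbers grow.

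**The case against.** The strongest reply is that this is a hypothetical co-intervention risk in a small open-label pilot. Several parts of it stand.

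- **The cited effects transfer poorly.** None is at 2 weeks and none concerns bupropion. The plan expects 30% cessation without texting, already above the 24% in the cited nicotine replacement arm. The table is an illustration.
- **A reader might infer that medication threatens a bias three times the texting effect**, since 16/5 = 3.2. The documents do not support that. Sixteen points is the largest of three contrasts and applies per treated woman, whereas 5 points is a difference between arms. Only the product with the uptake difference is comparable.
- **A reader might add chance imbalance in uptake to the bias.** That is ordinary sampling variation, which the test already covers and which reordering would not remove.
- **A reader might infer that the late baseline CO is itself a serious flaw.** It is an objective breath reading, narrated at enrolment, and bears mainly on the CO-change outcome. It is secondary.
- **Uptake may hardly vary.** Sections 2b and 9 describe medication as given in both arms, and it is free. But 2a and 3b make it conditional, so this reassurance depends on a contradiction that the plan has not resolved.
- **A woman's reaction to being offered texts could be counted as part of the strategy.** That is a legitimate choice of estimand, but the plan does not make it. Section 3b calls texting the only intervention, and section 9 says the experimental group receives the same care plus texts. The choice would also not cover a change in the staff's behaviour.

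**Conclusion.** The concern holds as a design weakness that can be reduced, and it is of modest size. As narrated, nothing prevents knowledge of the arm from shifting the initial medication decision, and an open-label design does not require this order. Under the cited contrasts, a 10-point uptake difference would distort the arm comparison by 0.6 to 1.6 points. Reproducing the whole 5-point target would take 31 to 83 points, and nothing in the documents suggests a shift of that size. The direction cannot be stated either: a reader might infer that the bias favours texting, but the documents give no basis for a sign.

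This rests on three assumptions: that the narrated order is the order of conduct, that the medication effect is additive and similar to the cited ones, and that uptake can differ between arms. In this pilot, sampling error would swamp the bias. The order still deserves correction, because the same bias would carry into any larger trial built on this procedure.

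**What to change.** 1. Open the envelope only at the end of the usual-care cessation visit, after baseline CO and the initial medication decision (patch, bupropion or none) have been recorded. No text is due before then. The clinical decision stays with the same people.
2. State that the exclusion for women who have already had the 30-minute pharmacy education (section 8h) is judged at consent. Otherwise counselling before allocation would conflict with it.
3. In the adjusted analysis of 3d, name the decision recorded before randomisation as the covariate, and do not adjust for later use.
4. Report initial and later medication use, and 2-week CO attendance, by arm.
5. Reconcile 2b and section 9 (medication in both arms) with 2a and 3b (medication conditional).

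The sample size does not change. The costs are real but small. Consent is taken at a standard-of-care visit (section 13) and the cessation consultation is scheduled separately (3b), so randomisation may move to the later visit. A few women may drop out before allocation. Recording a decision does not bind it, so later changes in medication are reduced at best, not prevented.

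The continuing-review box under Expedited Paragraphs marks remaining activity as data analysis only. If enrolment is closed, items 1 and 2 apply to a successor trial. Item 4 and the rule against adjusting for medication chosen after allocation can still be followed now, so far as the data were collected.
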